10.6 Safety Analyses

10.6.1 Adverse Events

Safety analyses will be conducted separately for phase 1b and phase 3. The Medical Dictionary for Regulatory Activities (MedDRA) version 20.0 or later will be used to code all adverse events (AE) to a system organ class and a preferred term. The CTCAE version 4.0 **or later** will be used to grade severity of adverse events. In general, events with missing IP relatedness, seriousness, or CTCAE severity grades are included in the analysis of treatment emergent AE as long as the event is satisfied for a TEAE.

However, analyses of treatment-related, SAE, or grade 3 or higher, or combination thereof will exclude events with missing relatedness, seriousness, and severity grades, respectively.

The subject incidence of AEs will be summarized for all treatment-emergent AEs, serious AEs, AEs leading to withdrawal of investigational product, grade 3 or 4 AEs, fatal AEs, talimogene laherparepvec events of interest (EOI) and pembrolizumab events of clinical interest (ECI). Subject incidence of EOIs and ECIs will be summarized by the EOI categories and ECI categories. Preferred terms within each EOI and ECI category will also be summarized.

The subject incidence of all treatment-related AEs, serious AEs, AEs leading to withdrawal of investigational product, grade ≥ 3 AEs, and fatal AEs will be tabulated by system organ class and preferred term in descending order of frequency.

Summaries of treatment-emergent and serious AEs occurring in at least 5% of the subjects by preferred term in any treatment arm will be provided in descending order of frequency.

A listing of fatal AEs will be provided. A listing of SAEs/EOIs/ECIs reported in the clinical database with an event onset after 30 days since last dose of IP will be provided. Listing of SAEs from consent and before first dose of study therapy will also be provided separately. Listing of SAEs reported with event onset 90 days after the last dose of study therapy or 30 days after last dose of study therapy if the subject initiates new anticancer therapy, whichever is earlier, will be provided. Additional listings of SAEs/EOIs/ECIs for subjects who received treatment by error that occur during the incorrect treatment period will be provided.

Potential or known unintended exposure to talimogene laherparepvec, related suspected signs or symptoms, and detection of talimogene laherparepvec in a subject's household member, caregiver, or healthcare provider will be summarized. Listings of reported cases with available qPCR testing results will be provided.

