10.5.4 Safety Endpoints

Treatment emergent adverse events are defined as adverse events that occur after receiving the first dose of study therapy through 30 days after the last dose of study therapy. Subject incidence rates of treatment-emergent adverse events (including all AEs, grade ≥ 3 AEs, SAEs, adverse events of interest and events requiring the discontinuation of study drug, local effects on the tumor [ie, pain, inflammation and ulceration]) will be summarized. Medical Dictionary for Regulatory Activities (MedDRA) will be used to code adverse events to a system organ class (SOC) and a preferred term

Approved

within the SOC. The CTCAE version 4.0 will be used to grade severity of adverse events. Adverse events reported beyond 30 days after the last dose will be analyzed separately.

The analyses of safety laboratory endpoints and vital signs will include summary statistics over time by treatment group. Shifts in grades of safety laboratory values between the baseline and the worst on-study value will be tabulated by treatment group.

Summary statistics will also be provided for concomitant medications, dose delay, study treatment discontinuation, overall exposure, and changes in ECOG performance status. Tables and/or narratives of deaths through either the 30 days after the last dose of talimogene laherparepvec or pembrolizumab, whichever is later, will be provided.

The ECG measurements from this clinical study will be performed as per standard of care for routine safety monitoring, rather than for purposes of assessment of potential QTc effect. Since these evaluations may not necessarily be performed under the rigorous conditions expected to lead to meaningful evaluation of QTc data, summaries and statistical analyses of ECG measurements are not planned, and these data would not be expected to be useful for meta-analysis with data from other trials.

The qPCR analysis result of talimogene laherparepvec DNA in swab samples taken from cold sore, vesicles and other lesions suspected to be herpetic in origin (if any) will be summarized descriptively. The incidence and percentage of subjects who develop anti-pembrolizumab antibodies (binding and if positive, neutralizing) at any time will be tabulated.

Potential or known unintended exposure to talimogene laherparepvec, related suspected signs or symptoms, and detection of talimogene laherparepvec in a subject's household member, caregiver, or healthcare provider will be reported.

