Pembrolizumab will be administered until confirmed iPD per modified irRC-RECIST (protocol Appendix F), intolerance to treatment, 24 months from the date of the first dose

of pembrolizumab, or end of study, whichever occurs first. Discontinuation of treatment may be considered for subjects who have attained a confirmed iCR and have been treated for at least 24 weeks with pembrolizumab and had at least 2 treatments with pembrolizumab beyond the date when the initial CR was declared.

At least **seven** interim analyses for safety, efficacy and futility are planned to be reviewed by a Data Monitoring Committee (DMC). Refer to [Section 8](#) for details on interim analyses.

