Measurable tumor burden is defined as the sum of the diameters (longest for non-nodal lesions, short axis for nodal lesions) for all target lesions and up to 10 (maximum 5 per organ) new measurable lesions. The measurable tumor burden will be censored at the start of the first subsequent anticancer therapy, or at the time of complete or partial removal/reduction of any target lesion which contained melanoma on pathology evaluation or pathology results were unknown, whichever occurs first.

Depth of Response (DpR)

DpR is defined based on the maximum post-baseline measurable tumor burden decrease from baseline measurable tumor burden where maximum post baseline-measurable tumor burden decrease is categorized as: G0 = no shrinkage or increase, G1 = $>0 \leq 25\%$, G2 = $>25-50\%$, G3 = $>50-75\%$, G4 = $>75- < 100\%$, and G5 = 100%.

End of Study

Primary Completion: The primary completion date is defined as the date when the last subject is assessed or receives an intervention for the purposes of final collection of data for the primary endpoint(s).. The primary completion date is the date when data for the primary endpoints are last collected for the purpose of conducting the primary analysis.

If the study concludes prior to the primary completion date originally planned in the protocol (ie, early termination of the study), then the primary completion will be the date when the last subject is assessed or receives an intervention for evaluation in the study (ie, last subject last visit).

End of Study: The end of study date is defined as the date when the last subject across all sites is assessed or receives an intervention for evaluation in the study (ie, last subject last visit), following any additional parts in the study (eg, long term follow-up), as applicable.

Evaluable tumor assessment

An overall visit response other than iUE or UE.

Event of Interest (EOI) and Events of Clinical Interest (ECI)

EOIs are defined in version-controlled search strategies maintained by Global Regulatory Affairs and Safety (GRAAS) at Amgen for talimogene laherparepvec and those for ECIs for pembrolizumab will be provided by Merck before the analysis.

Investigational product (IP)

Investigational product (IP) refers to talimogene laherparepvec/placebo (also known as “Amgen IP”) and Pembrolizumab (also known as “non-Amgen IP”) in this study. IP is also referred as study drug, or study therapy.

Last date known to be alive

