Treatment-emergent adverse events are defined as any adverse event occurring after initiation of the first dose of study therapy through 30 days after the last administration of study therapy. Adverse events that occur on the same day as the first dose date of study therapy will be treated as treatment emergent events unless indicated otherwise (for example, if an event occurs on the same date as the first administration of study therapy and the check box indicating prior to the first dose of study therapy is checked on eCRF, then the event will not be counted as a treatment-emergent AE).

Treatment-emergent serious adverse events (TESAE)

Treatment-emergent serious adverse events are defined as any serious adverse event occurring after initiation of the first dose of study therapy through 90 days after the last administration of study therapy or 30 days after the last administration of study therapy if the subject initiates new anticancer therapy, whichever, is earlier. Serious adverse events that occur on the same day as the first dose date of study therapy will be treated as treatment emergent serious events unless indicated otherwise (for example, if an event occurs on the same date as the first administration of study therapy and the check box indicating prior to the first dose of study therapy is checked on eCRF, then the event will not be counted as a treatment-emergent serious adverse event).

7. Analysis Subsets

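### Adverse events are compared between arms only by crude incidence over a window that follows dosing, so added toxicity cannot be told apart from longer observation for late or steadily accruing events

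*SAP*

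**What the plan says.** **Measure.** SAP 10.6.1 states that "The subject incidence of AEs will be summarized for all treatment-emergent AEs, serious AEs", followed by events leading to withdrawal, grade 3 or 4, fatal, and the two special-interest categories. Treatment-related events are tabulated the same way. Protocol 10.5.4 likewise plans "Subject incidence rates of treatment-emergent adverse events".

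**Window.** SAP Section 6 defines a treatment-emergent event as "any adverse event occurring after initiation of the first dose of study therapy through 30 days after the last administration of study therapy". Treatment-emergent serious events run to 90 days, or to "30 days after the last administration of study therapy if the subject initiates new anticancer therapy", whichever is earlier. The same section says "IP is also referred as study drug, or study therapy", and IP covers both the injected product and pembrolizumab, so the window follows whichever stops last.

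**What ends dosing.** In SAP 3.1.2, pembrolizumab continues "until confirmed iPD per modified irRC-RECIST (protocol Appendix F), intolerance to treatment", 24 months or end of study. "Discontinuation of treatment may be considered for subjects who have attained a confirmed iCR", after at least 24 weeks of pembrolizumab. Injections also stop at complete response or when no injectable lesion remains. Protocol 3.1.3.3 allows dosing beyond confirmed iPD by exception.

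**Outside the window.** Protocol 10.5.4 adds: "Adverse events reported beyond 30 days after the last dose will be analyzed separately". SAP 10.6.1 gives listings of later serious and special-interest events.

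**Exposure.** SAP 10.6.6 summarises doses and duration for each product. Neither document connects these figures to adverse events, and neither plans a time-to-first-event or fixed-time cumulative incidence of adverse events.

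**The concern.** The phase 3 safety objective compares the regimens by incidence of adverse events. If the combination delays progression, as the trial hypothesises, its subjects are dosed and counted for longer. An event with the same hazard in both arms then shows a higher percentage on the combination. The crude table would not say whether the excess is toxicity or time. The exposure table would show the imbalance but not how much of the excess it explains.

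The question matters for events that come late or accrue steadily. Immune-related events are candidates: protocol 6.2.2.2 notes that they may appear soon after the first dose or months after the last. It matters little for early injection reactions. No safety hypothesis is tested, so type I error is not involved.

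**Working it through.** **Inputs from protocol 10.2.2.** Control PFS is 0.95, 0.60, 0.49, 0.39, 0.32 and 0.30 at 1.5, 3, 6, 12, 18 and 24 months, with constant hazard within intervals. The design HR is 2/3 for PFS and 0.60 for iPFS. Assumed complete response rates are 6% on control and 20% on the combination. Dosing is capped at 24 months.

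**Assumptions not in the documents.** RECIST PFS stands in for time on treatment, since no curve is given for confirmed iPD. The control event rate is set at 30%. Event hazards are identical in the two arms.

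**Reproducing the plan.** Events = 4(2.807 + 1.282)² / (ln 1.5)² = 406.7, so 407 as stated. The curve gives medians of 5.7 and 15.0 months, against the stated 5.6 and 15.0.

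**Mean window.** The area under each piece is width × (Sa − Sb) / ln(Sa/Sb), with the combination curve S^(2/3).
- Control: 1.462 + 1.142 + 1.629 + 2.629 + 2.123 + 1.859 = 10.84 months.
- Combination: 1.475 + 1.249 + 1.996 + 3.459 + 3.001 + 2.748 = 13.93 months.
- Adding 30 days (0.99 month): 11.83 vs 14.91 months, a ratio of 1.26.

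**Crude incidence.** With W the window and T the time for which the hazard lasts, incidence = E[1 − exp(−λ·min(W, T))]. For a constant hazard, 30% on control gives λ = 0.0345 per month. Readings on the combination with no true difference are:

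| Setting | Combination |
|---|---|
| HR 2/3, hazard lasts 3 / 6 / 12 months | 30.3% / 32.0% / 34.1% |
| HR 2/3, constant hazard | 36.6% |
| HR 0.60, constant hazard | 38.2% |
| HR 0.8, constant hazard | 33.7% |
| HR 2/3, constant, stopping 28 or 84 days after progression (confirmation) | 36.0% or 34.9% |
| HR 2/3, constant, all complete responders stop at about month 6 | 31.5% to 32.3% |
| HR 2/3, constant, confirmation delay and all complete responders stopping | 30.3% to 31.7% |
| HR 1 | 30% |

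In the joint row the mean window is about 1% to 7% longer. The low end uses an 84-day delay, with complete responders drawn from those progression-free at 24 months. The high end uses a 28-day delay, with complete responders drawn at random from those progression-free at month 6.

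**Serious events.** With the 90-day tail the means are 13.8 vs 16.9 months and 30% reads 35.6%. If every progressor starts new therapy, so that the tail is cut to 30 days, the means are 12.4 vs 15.8 months and the reading is 36.9%.

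**Candidate summaries** (HR 2/3):
- Constant hazard, censoring at window end: 1 − exp(−0.0345τ) gives 18.7%, 33.9% and 56.3% at 6, 12 and 24 months in both arms.
- Constant hazard, window end treated as a competing event: 29.6% vs 36.0% remains at 24 months.
- Exposure-adjusted rate ratio with no true difference: 1 for a constant hazard, but 0.81, 0.86 and 0.93 when the hazard lasts 3, 6 and 12 months.

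**The case against.** The objective is incidence, and the plan delivers it. Exposure by arm is tabulated, later events are collected and reported, and no safety hypothesis is tested. Both arms receive pembrolizumab. The added product is an injection whose common reactions in its earlier phase 3 trial were chills, pyrexia and injection-site pain, and early reactions are essentially unaffected. No passage supports a flat hazard over two years. Confirmation takes 4 to 12 weeks, and complete responders, assumed more frequent on the combination, may stop early. Acting together these nearly close the gap. More stopping for intolerance on the combination, which is not modelled, would shrink it further. Any correction also needs assumptions of its own.

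Most of this stands, and it limits the size of the point. What it does not answer is that the planned tables cannot separate the two explanations if an excess appears.

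A reader might infer that the plan will show roughly 37% against 30% from longer observation alone. The documents do not support that: it needs a flat hazard, the full design effect, stopping exactly at RECIST progression and no stopping for response. Nor do all harms share a 30-day window, and dosing does not invariably stop at confirmed iPD.

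**Conclusion.** The gap is real and descriptive. Crude incidence is valid for the stated objective, but for late or steadily accruing events it cannot distinguish more toxicity from a longer counting window. The illustrative distortion for a 30% constant-hazard event runs from almost nothing to about 8 percentage points (30% to 38%), depending on the PFS effect, confirmation delay and how many complete responders stop. It vanishes at HR 1 and is about 0.3 points for events confined to the first 3 months at HR 2/3. All figures rest on PFS as a proxy for time on treatment and on an assumed 30% control rate. They show that the issue can arise, not that it will. This is a cheap improvement, not a defect that invalidates the safety analysis.

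**What to change.** Keep the crude tables. Add to SAP 10.6.1, as supportive and descriptive, for treatment-emergent, grade ≥3, serious, treatment-related and talimogene laherparepvec events of interest:

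> Cumulative incidence of first event by arm at 6, 12 and 24 months, with death as a competing event, censoring at the end of the relevant treatment-emergent window, and the number of subjects still in the window at each time.

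The window-end rule must be written down, because treating window end as a competing event would leave the artefact in place. Label the result as an estimate as if dosing continued. It is not the share of subjects who had the event: in the example it gives 56.3% at 24 months where 30% of control subjects were affected. State that censoring is doubtful for subjects who stop for intolerance. Exposure-adjusted rates may be shown alongside but not alone, since they overcorrect for early events. Curves for pembrolizumab events of clinical interest are unnecessary, because protocol 9.5 limits these to overdose and a liver-test threshold.

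The cost is a few tables from onset and dosing dates already collected. Under the proxy at HR 2/3, about 173 vs 214, 134 vs 181 and 100 vs 149 of 330 per arm would still be in the 30-day window at the three times.

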9.2 Safety Event Reporting Procedures

9.2.1 Adverse Events

9.2.1.1 Reporting Procedures for Adverse Events That do not Meet Serious Criteria

The investigator is responsible for ensuring that all adverse events observed by the investigator or reported by the subject that occur after first dose of talimogene laherparepvec/placebo or pembrolizumab through the safety follow-up visit (ie, 30 [+7] days after the last dose of talimogene laherparepvec/placebo or pembrolizumab, whichever is later, are reported using the applicable CRF (eg, Adverse Event Summary). In addition, injected investigational product-related adverse events that occur during the long term safety follow-up period until the end of study should also

be captured in the Adverse Event CRF although these events will not be considered treatment-emergent adverse events.

The investigator must assign the following adverse event attributes:

- Adverse event diagnosis or syndrome(s), if known (if not known, signs or symptoms),
- Dates of onset and resolution (if resolved),
- Severity [and/or toxicity per protocol],
- Assessment of relatedness to injected investigational product and/or pembrolizumab, and
- Action taken.

The adverse event grading scale used will be the CTCAE version 4.0. The grading scale used in this study is described in [Appendix A](#). The investigator must assess whether the adverse event is possibly related to injected investigational product and/or pembrolizumab. This relationship is indicated by a “yes” or “no” response to the question: Is there a reasonable possibility that the event may have been caused by injected investigational product and/or pembrolizumab?

The investigator must assess whether the adverse event is possibly related to any study-mandated activity and/or procedure (including any screening procedures). This relationship is indicated by a “yes” or “no” response to the question: “Is there a reasonable possibility that the event may have been caused by a study activity and/or procedure”?

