10.1.1.2 Secondary Endpoints

Phase 1b:

- Confirmed ORR (CR+PR) (response evaluation by investigator using modified irRC).
- BOR, DRR (duration of response for 6 months or longer), DOR (the time from date of the initial confirmed response to the date of the first documented PD or death), DCR, and PFS (response evaluation by investigator using modified irRC).
- OS.
- Incidence of treatment-emergent and treatment-related adverse events (all AEs, grade ≥ 3 AEs, SAEs, fatal AEs, AEs defined as events of interest), and abnormal laboratory tests.

Phase 3:

- iCRR by blinded independent central review using modified irRC-RECIST
- iPFS by blinded independent central review using modified irRC-RECIST
- OS in subjects excluding stage IVM1c per CRF
- ORR (CR + PR), BOR, DRR, DOR (the time from date of the initial confirmed response to the date of the first documented PD or death), and DCR (response evaluation by blinded independent central review using modified RECIST 1.1), and iORR (iCR + iPR), iBOR, iDRR, iDOR, and iDCR response evaluation by blinded independent central review using modified irRC-RECIST).
- Incidence of treatment-emergent and treatment-related adverse events (all AEs, grade ≥ 3 AEs, SAEs, fatal AEs, and AEs defined as events of interest), and abnormal laboratory tests.
- Changes in EORTC QLQ-C30 GHS/QoL subscale.

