8.1.2 Interim Safety Analysis (Phase 3)

An independent Data Monitoring Committee (DMC) will review interim safety analyses to evaluate the safety of talimogene laherparepvec in combination with pembrolizumab in the target population for the phase 3. The first two safety analyses occurred after approximately 20 and 100 total subjects had enrolled in phase 3, respectively, who had

the opportunity to be followed for at least 6 weeks after initiating study treatment. Additional safety review meetings may occur every 6 months after the interim iORR and iDCR futility review meeting (Section 8.1.3) until the primary analysis of OS. Unblinded safety tables and listings by treatment arm will be prepared for the DMC by IBG according to the DMC charter. All available safety data from the phase 1b part of the study was provided to DMC at the time of the first planned interim safety analysis (ie, at 20 subjects trigger) in phase 3.

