10.6.3 Vital Signs

Analysis of vital signs will not be performed as routine monitoring and collection of vital sign data is not sufficient for analysis.

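### SAP 10.6 narrows or drops safety analyses set out in Protocol 10.5.4 (late related AEs, all-causality grade ≥ 3, laboratory and vital-sign summaries), and SAP section 11 records no change

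*SAP*

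**What the plan says.** **Late AEs.** Protocol 9.2.1.1 has sites record "injected investigational product-related adverse events that occur during the long term safety follow-up period until the end of study" on the AE form. It sets no seriousness limit and states that these events do not count as treatment-emergent. Protocol 10.5.4 adds: "Adverse events reported beyond 30 days after the last dose will be analyzed separately". SAP 10.6.1 answers with listings: "A listing of SAEs/EOIs/ECIs reported in the clinical database with an event onset after 30 days since last dose of IP will be provided". A further listing covers SAEs with onset after the serious-event reporting window.

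**Grade.** The secondary endpoint in Protocol 10.1.1.2 is "Incidence of treatment-emergent and treatment-related adverse events (all AEs, grade ≥ 3 AEs, SAEs, fatal AEs, and AEs defined as events of interest"; SAP 4.1.2 repeats it, and Protocol 10.5.4 plans treatment-emergent incidence at grade ≥ 3. The treatment-emergent summary in SAP 10.6.1 instead lists "AEs leading to withdrawal of investigational product, grade 3 or 4 AEs, fatal AEs". The next paragraph does tabulate grade ≥ 3 AEs, but it opens with treatment-related events.

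**Laboratory and vital signs.** Protocol 10.5.4: "The analyses of safety laboratory endpoints and vital signs will include summary statistics over time by treatment group". SAP 10.6.3: "Analysis of vital signs will not be performed", with the reason that routine collection is not adequate for the purpose. SAP 10.6.2 keeps grade shifts from baseline and adds Hy's Law and investigator-confirmed liver-injury incidence. It has no summaries over time.

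**Declared changes.** SAP section 11, which should list departures from the protocol's analyses, is marked as not applicable.

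**The concern.** Safety incidence is a stated secondary endpoint of phase 3, and the SAP is where it becomes actual output. The late related AEs matter most. The Amendment 2 summary in the protocol gives the reason for collecting them: subjects may spend years in long-term follow-up before they can join the separate registry. If the SAP is programmed as written, part of what was collected for that purpose has no assigned place in the report.

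The grade wording raises a different problem. The quantity named in the endpoint may not appear for all-causality events, and the all-causality and treatment-related displays may use different grade cut-offs.

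The section 11 entry makes each item worse than it need be. A descriptive output can reasonably be dropped if the change is recorded. A statement that nothing changed, when several things did, invites questions about prespecification that could be avoided.

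**Working it through.** No sample size, power or alpha figure is involved. The check is a comparison of passages, plus two short pieces of arithmetic.

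**1. Where would a late, non-serious, related AE appear?** Take an event related to the injected product, non-serious, with onset more than 30 days after the last dose, and outside the events of interest (EOI) and pembrolizumab events of clinical interest (ECI). Test it against each AE output in SAP 10.6.1:

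- Treatment-emergent summaries: excluded. The SAP section 6 window closes at 30 days, and Protocol 9.2.1.1 says such events are not treatment-emergent.
- Serious AE summary: excluded as non-serious. (SAP section 6 runs the treatment-emergent serious window to 90 days, or 30 days if new anticancer therapy starts, so some later SAEs may be summarised by arm. Protocol 10.5.4 uses 30 days throughout. This is another difference not recorded in section 11.)
- Summaries of events in at least 5% of subjects: excluded, because they cover treatment-emergent and serious events.
- Post-day-30 listings: excluded, because they cover SAEs, EOIs and ECIs.
- Table of all treatment-related AEs: unclear, because no time window is stated. If late events are in, they are pooled with on-treatment events. If they are out, they are absent. Neither is the separate analysis that the protocol describes.

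How many events fall outside the EOI and ECI terms cannot be judged. SAP section 6 places the EOI search strategies outside the SAP and says that those for ECIs will be supplied before the analysis. Protocol 9.5 names two ECIs: pembrolizumab overdose and a liver-test threshold.

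**2. How long is the late window?** Inputs: follow-up of about 60 months after the last randomization and treatment of up to about 24 months (Protocol 3.5.1); the 30-day treatment-emergent window, taken as 1 month; enrollment of 26 months (Protocol Table 9).

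- Last subject randomized, full treatment: 60 − 24 − 1 = 35 months, which is 35/60 = 58% of that subject's follow-up.
- First subject randomized, stopping almost at once: 26 + 60 − 1 = 85 months.

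These are calendar windows for a subject who survives and stays in follow-up. They are not event counts.

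**3. Can grade ≥ 3 incidence be rebuilt from the two rows?** Let a be the number of subjects with a grade 3 or 4 treatment-emergent AE, b the number with a fatal one, and c the number with both. The endpoint count is a + b − c, with 0 ≤ c ≤ min(a, b). So max(a, b) ≤ count ≤ a + b. The summary gives a and b but not c, so the count is not determined.

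The later grade ≥ 3 table has two readings. If the word treatment-related governs only the first item in its list, all-causality grade ≥ 3 is tabulated. If it governs every item, it is not. The text does not settle this.

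**4. Laboratory and vital signs.** The protocol sentence covers both types of data. The laboratory shift tables survive. The laboratory summaries over time and the whole vital-sign analysis do not.

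**5. Section 11.** Items 1, 3 (on the narrower reading) and 4 all differ from Protocol 10.5.4, and none is recorded there.

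**The case against.** The other side has substance.

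- **Late safety is not unreported.** Late SAEs are listed, and late EOIs and ECIs are listed whatever their seriousness. The treatment-related table may include late events. Viral DNA in suspected herpetic lesions and unintended exposures are reported, and a separate registry follows late related events. All of this stands. It narrows the gap to non-serious related events outside the search terms and to the missing by-arm late summary. It does not supply the protocol's separate analysis.
- **Grade ≥ 3 is in the SAP.** It is the endpoint in SAP 4.1.2, it is tabulated in the paragraph after the disputed phrase, and SAP 9.3 and 10.6.1 refer to analyses of grade 3 or higher. Fatal AEs keep their own row and a listing. This stands against any claim that the endpoint was replaced or deaths concealed. The ambiguity about causality remains.
- **The vital-sign omission is open and reasoned.** True, and it may be a sound decision. What is missing is the entry in section 11.
- **These are descriptive outputs.** True. No hypothesis test, alpha or safety decision rule is affected.

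A reader might also take SAP 8.1.2, "Additional safety review meetings may occur every 6 months", as weakening the firm six-monthly safety reviews by the data monitoring committee in Protocol 3.1.2 and 10.4.1.2. SAP wording does not cancel a protocol commitment, and the committee works to its own charter. This is a minor passage to reconcile.

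**Conclusion.** The concern holds in a limited form. SAP 10.6 does not deliver three parts of Protocol 10.5.4 as written: the separate analysis of AEs beyond 30 days, an unambiguous all-causality grade ≥ 3 incidence, and the vital-sign and laboratory summaries over time. Section 11 says that nothing changed. It should be corrected before the study team's analysis. It does not touch efficacy or error control.

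The late window is about 35 to 85 months per subject, on the follow-up, treatment and enrollment durations in the protocol. The number of events affected is unknown, because the search strategies are not in the documents and no late event rate is given.

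Three stronger readings are not supported:

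- That the trial cannot report the late safety of the virus. Several late outputs exist.
- That the wording makes toxicity look lower. Subjects whose only severe event is fatal still appear in the fatal row, the same rule applies to both arms, and no effect on the comparison is shown.
- That the grade effect can be sized from the fatal AEs in the earlier phase 3 trial described in Protocol 2.2. The documents do not say how many of those subjects also had a grade 3 or 4 event, and that was an open-label comparison with GM-CSF, not a blinded combination with pembrolizumab.

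**What to change.** In SAP 10.6.1:

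- Add a by-arm table and a listing of all AEs related to the injected product with onset more than 30 days after the last dose, serious or not, by preferred term and grade.
- In the treatment-emergent summary, replace the grade 3 or 4 category with grade ≥ 3, keeping the fatal row.
- State the time window of the treatment-related table, and whether its grade ≥ 3 line is limited to related events.

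In SAP 10.6.2 and 10.6.3, restore the laboratory and vital-sign summaries over time, or record their removal with reasons in section 11. Record the wider serious-event window there too. Bring SAP 8.1.2 into line with Protocol 3.1.2 and 10.4.1.2.

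The cost is a short SAP amendment and a few extra outputs from data already collected. Nothing changes for sites or subjects.
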